18.3.1. ECG SPECIFIC DERIVATIONS

Not applicable.

18.3.2. ECG CATEGORIES

Markedly abnormal quantitative ECG measurements will be identified in accordance with the following predefined criteria:

[figure not shown]
- Absolute values for QTcF will be classified as:
 - > 450 msec
 - > 480 msec
 - > 500 msec
- Change from Baseline for QTcF will be classified as:
 - > 30 msec increase from Baseline
 - > 60 msec increase from Baseline

Predefined treatment-emergent categories will be presented in tables where the incidence rate will be based on the total number of patients ‘at risk’, for example:

- If a criterion involves a change from baseline, evaluable patients would have both a pre-dose and at least one post-dose value recorded.

Document:	\\weedc-vnasc01\BIOSdata\F2G\F901318\		
Author:		Version Number:	3.0
		Version Date:	06Apr2023
Template No.:	CS_TP_BS016 Revision 6	Reference:	CS_WI_BS005
Effective Date:	02Dec2019		

F2G Ltd.
PROTOCOL F901318/0032

- If a criterion does not consider change from baseline, to be evaluable the patient need only have one post-dose value recorded.
- Central overreads of ECG data began part way through the study. Summaries of QTcF, incidence of prolongation and spaghetti plot for absolute QTcF over time will be provided for ECG prospective central and retrospective central assessments.

18.4. VITAL SIGNS

The following Vital Signs measurements will be reported for this study:

- Systolic Blood Pressure (mmHg)
- Diastolic Blood Pressure (mmHg)
- Pulse Rate (bpm)
- Respiratory Rate (breaths/min)
- Body Temperature (°C)
- Height (cm)
- Weight (kg)
- BMI (kg/m²) [derived]

The following summaries will be provided for vital signs data:

- Table and box-and-whiskers plot of actual and change from baseline value descriptive statistics by visit
- Incidence of treatment-emergent markedly abnormal values
- Listing of vital signs

18.4.1. VITAL SIGNS SPECIFIC DERIVATIONS

- $BMI (kg/m^2) = weight (kg) / [height (m)]^2$
- Body Temperature may be recorded in either °C or °F. For summarization purposes, °F will be

Document: \\weedc-vnasc01\BIOSdata\F2G\F901318\ [Redacted]
Author: [Redacted] Version Number: 3.0
Version Date: 06Apr2023
Template No.: CS_TP_BS016 Revision 6 Reference: CS_WI_BS005
Effective Date: 02Dec2019

F2G Ltd.
PROTOCOL F901318/0032

converted to °C as follows:

- Body Temperature in °C = (Body Temperature in °F – 32) × 5/9
- Height may be recorded in either cm or inch. For summarization purposes inch will be converted to cm as follows:
- Height in cm = Height in inch × 2.54

18.4.2. VITAL SIGNS MARKEDLY ABNORMAL CRITERIA

Predefined treatment-emergent abnormalities will be presented in tables where the incidence rate will be based on the total number of patients ‘at risk’, for example:

- If a criterion involves a change from baseline, evaluable patients would have both a pre-dose and at least one post-dose value recorded.
- If a criterion does not consider change from baseline, to be evaluable the patient need only have one post-dose value recorded.

Markedly abnormal quantitative Vital Signs measurements will be identified in accordance with the following predefined markedly abnormal criteria:

Variable (Unit)	Low	High
Systolic Blood Pressure (mmHg)	NA	Hypertension-SBP>=140
Diastolic Blood Pressure (mmHg)	NA	DBP>=80
Pulse rate (BPM)	Sinus bradycardia: <60	Sinus tachycardia: >100 Supraventricular tachycardia: >100 Ventricular tachycardia: >100
Body temperature (°C)	Hypothermia<=35(grade 2)	Fever >=38 (grade 1)
Weight (kg)	Weight Loss- percentage change from baseline ≤ - 5.0 %	Weight Gain- percentage change from baseline ≥ 5.0 %

Document: \\weedc-vnasc01\BIOSdata\F2G\F901318\ [Redacted]
 Author: [Redacted] Version Number: 3.0
 Version Date: 06Apr2023
 Template No.: CS_TP_BS016 Revision 6 Reference: CS_WI_BS005
 Effective Date: 02Dec2019

NA-Not Available.

In the event that a vital sign value does not comply with the criterion for classification as Low or High, the value will be categorised as normal.

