8.9.4 Vital Signs Measurements, ECG, Physical Findings and Other Safety Evaluations

8.9.4.1 Vital Signs

Vital signs (systolic blood pressure, diastolic blood pressure, pulse rate, respiratory rate, body temperature, weight and BMI) will be summarised using descriptive statistics at each visit for observed data and change from baseline.

Pre-defined treatment-emergent abnormalities (newly occurring), as defined by CTCAE criteria, will be presented in tables and listed, where the incidence rate will be based on the total number of patients 'at risk' (see example in Section 8.9.3).

A similar approach as for laboratory values will be followed for vital signs with regards to retests and values not complying with CTCAE criterion.

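### SAP 18.4.2 puts three tachycardia diagnoses on one pulse cut-off and sets no low blood pressure criterion, yet classes every unflagged value as normal

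*SAP*

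**What the plan says.** SAP 18.4 lists the vital signs to be reported, including systolic and diastolic pressure, pulse rate and respiratory rate. One of its planned outputs is "Incidence of treatment-emergent markedly abnormal values". SAP 18.4.2 supplies the criteria for that output: "Markedly abnormal quantitative Vital Signs measurements will be identified in accordance with the following predefined markedly abnormal criteria".

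- **Pulse rate.** The Low entry is "Sinus bradycardia: <60". The High entry is "Sinus tachycardia: >100 Supraventricular tachycardia: >100 Ventricular tachycardia: >100".
- **Systolic pressure.** The Low entry is NA. The High entry is "Hypertension-SBP>=140".
- **Diastolic pressure.** The Low entry is NA. The High entry is a value of 80 mmHg or more.
- **Respiratory rate.** There is no row.

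The note under the table expands the abbreviation: "NA-Not Available". The empty Low entries are therefore the plan's own content and not a redaction. A default rule covers values that meet neither criterion: "does not comply with the criterion for classification as Low or High, the value will be categorised as normal".

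Protocol 8.9.4.1 describes the corresponding output as "Pre-defined treatment-emergent abnormalities (newly occurring), as defined by CTCAE criteria". It also says that values not meeting a CTCAE criterion are handled much as laboratory values are, and Protocol 8.9.3 classes such laboratory values as normal.

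**The concern.** Two features of the table can mislead a reader of the safety output.

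First, a pulse taken as a vital sign gives a rate. It does not show where the rhythm arises. Attaching a ventricular rhythm diagnosis to a rate criterion puts a serious cardiac term in a safety table with no ECG evidence behind it. The study excludes patients at high risk of QT prolongation unless the Medical Monitor approves (Protocol 4.3.2), and it tabulates QTcF prolongation (SAP 18.3.2). A ventricular tachycardia entry alongside those results would draw attention it has not earned. The Low label for pulse has the same fault in milder form, since sinus bradycardia is also a rhythm diagnosis.

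Second, with no low limit for blood pressure and a default class of normal, a very low reading is actively labelled normal rather than left unclassified. These patients are seriously ill and low pressure is a plausible event among them.

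According to SAP 4.3, the initial analysis receives every output planned for the final analysis. The table would therefore appear in both reports.

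**Working it through.** The plan states no figure on this point, so there is nothing to reproduce. The check applies the SAP 18.4.2 rules literally and compares the result with the sections that might repair it.

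**1. Rules, all from SAP 18.4.2.** Pulse: Low if <60; High if >100, under each of three labels. Systolic: High if ≥140. Diastolic: High if ≥80. Anything else: normal.

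**2. Application.**

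| Measurement | Value | Category as written |
|---|---|---|
| Pulse (bpm) | 55 | Low: sinus bradycardia |
| Pulse | 60, 80, 100 | normal |
| Pulse | 101, 110, 150 | High: sinus, supraventricular and ventricular tachycardia |
| Systolic (mmHg) | 50, 70, 90, 139 | normal |
| Systolic | 140 | High |
| Diastolic (mmHg) | 30, 40, 60, 79 | normal |
| Diastolic | 80 | High |
| Respiratory rate | any | no criterion given |

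**3. Pulse labels.** Each of the three labels selects the same set, patients with a pulse >100, so n(sinus) = n(supraventricular) = n(ventricular). Over all whole-number pulses from 30 to 200 bpm, no value meets one label without meeting the other two. The labels carry no information beyond the cut-off.

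**4. Blood pressure.** All whole-number systolic values from 0 to 139 and diastolic values from 0 to 79 fall in the normal class. No reading, however low, can be flagged.

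**5. Respiratory rate.** It is measured (Protocol 6.4.3.1) and reported (SAP 18.4). Without a row, either it is left out of the incidence table or every value falls to the default. The SAP does not say which.

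**6. Whether another section repairs this.**

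- SAP 18.3 lists heart rate, ECG intervals, QTcF and an overall investigator judgment of normal or abnormal. SAP 18.3.2 gives categories for QTcF only. Neither contains a rhythm variable that could separate the three labels.
- The legible entries in SAP 3.3, the list of changes from the protocol, do not mention the vital-sign criteria or any departure from the CTCAE basis in Protocol 8.9.4.1.
- The SAP version history records that the systolic high limit was amended in version 2.0 on safety physicians' advice. It records no source for the other limits and no low limit.

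**The case against.** The strongest reply has four parts.

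*The labels may be only a caption.* SAP 8 says the accompanying templates fix the format and content of the tables, and those templates are not in the documents. SAP 18.4.2 sorts values into Low and High, and all three labels sit in one High cell. A single High row for pulse fits the text too. This stands. A reader might infer that the report will contain a separate count of ventricular tachycardia patients, but the documents do not establish that. What they establish is that the written rule assigns that label, and a single row captioned with it would still be wrong.

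*Low pressure is visible elsewhere.* SAP 18.4 also requires by-visit tables, box plots and a listing, and SAP 6 includes the minimum among the descriptive statistics. Protocol 6.4.1 makes clinically significant vital-sign results adverse events, and SAP 18.1.1 tabulates those. This largely stands, with two limits. SAP 6.4 keeps unscheduled measurements out of by-visit summaries. Protocol 6.4.1 also excludes abnormal findings associated with the underlying disease unless they are more severe than expected. Neither by-visit minima nor listings count the patients affected.

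*The normal default comes from the protocol.* Protocol 8.9.3 and 8.9.4.1 set that convention. This stands, so changing the wording is a departure to be recorded. The convention misleads most where a variable has no criterion at all on one side, as with low pressure here.

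*It is one descriptive table.* It feeds no endpoint, analysis set or test, and IDSMB displays are specified separately (SAP 4.1). This stands and limits the severity.

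**Conclusion.** The defect is real and limited. As written, SAP 18.4.2 assigns three rhythm diagnoses to a criterion that cannot tell them apart. It also leaves low blood pressure and respiratory rate without a category while labelling unflagged values normal. The structural results rest only on the SAP text: identical counts for the three labels, and no systolic value below 140 or diastolic value below 80 ever flagged. The statement that patients would be reported under ventricular tachycardia rests on literal programming, because the table templates are not available.

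Two stronger conclusions are not supported. A reader might infer a large number of falsely labelled patients. The documents give no rate of pulse above 100, and the output is limited to treatment-emergent values, newly occurring in the protocol's wording, so patients already above 100 at baseline may not count. No patient number can be given. A reader might also infer that the study reports a zero incidence of hypotension. The table has no low category, so it reports no such incidence, and the adverse event tables can still report one.

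The primary endpoint is unaffected. This should be fixed, but it does not threaten the study's main conclusions.

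**What to change.** 1. In SAP 18.4.2, replace the pulse entries with two neutral rows, 'Pulse rate >100 bpm' and 'Pulse rate <60 bpm', with no rhythm terms. Take rhythm diagnoses only from ECG findings and coded adverse events.
2. Replace the default class normal with 'criterion not met'. Record this in SAP 3.3 as a departure from the convention in Protocol 8.9.3 and 8.9.4.1.
3. Have the sponsor's safety physicians reconcile the table with the CTCAE basis in Protocol 8.9.4.1 and pre-specify low-pressure and respiratory-rate categories. No values are proposed here. Where the agreed criteria depart from CTCAE, record that in SAP 3.3 as well.
4. Check that the table template carries the same labels as the amended section.

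The cost is a SAP table edit, entries in SAP 3.3, a short consultation with the safety physicians and one programming change. Pulse, blood pressure and respiratory rate are already collected, so no new data are needed.

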18.5. HOSPITALIZATION RECORDS

The following hospitalization records will be reported for this study:

- Event type
- Date of Ward Change, Hospital Admission/Re-admission, Discharge
- Type of Ward or discharge Destination
- Reason for Ward Change, Hospital Admission/Re-admission, Discharge
- Was the Change Associated with the Enrolling Fungal Infection
- Outpatient Healthcare Services
 - Number of outpatient office/clinical visits
 - Number of visits to emergency department that did not lead to hospitalization
 - Number of home care visits provided by medical professionals
 - Type of service

The following summaries will be provided for hospitalization records data:

- Incidence of hospitalization events, types of ward/discharge destinations and types of healthcare services received
- Listing of hospitalization records

18.6. PHYSICAL EXAMINATION

Physical examination findings will only be presented in data listings.

Document: \\weedc-vnasc01\BIOSdata\F2G\F901318\ [Redacted]
Author: [Redacted] Version Number: 3.0
Version Date: 06Apr2023
Template No.: CS_TP_BS016 Revision 6 Reference: CS_WI_BS005
Effective Date: 02Dec2019

[REDACTED]

F2G Ltd.
PROTOCOL F901318/0032

18.7. [REDACTED]

[REDACTED]

- [REDACTED]
- [REDACTED]

[REDACTED]

- [REDACTED]
- [REDACTED]
- [REDACTED]

18.8. PREGNANCY TEST

Pregnancy test data will only be presented in data listings.

19. [REDACTED]

[REDACTED]

[REDACTED]

[REDACTED]

[REDACTED]

20. DATA NOT SUMMARIZED OR PRESENTED

The other variables and/or domains not summarized or presented are:

- Laboratory sample collection information, for example accession number.
- Data resulting from sample shipments made to central laboratories, as captured on the Central Lab Shipment eCRF page.

Document: \\weedc-vnasc01\BIOSdata\F2G\F901318 [REDACTED]
Author: [REDACTED] Version Number: 3.0
Version Date: 06Apr2023
Template No.: CS_TP_BS016 Revision 6 Reference: CS_WI_BS005
Effective Date: 02Dec2019

[REDACTED]

F2G Ltd.
PROTOCOL F901318/0032

These domains and/or variables will not be summarized or presented, but will be available in the clinical study database, Study Data Tabulation Model (SDTM) and/or Analysis Data Model (ADaM) datasets.

APPENDIX 1. PROGRAMMING CONVENTIONS FOR OUTPUTS

OUTPUT CONVENTIONS

Outputs will be presented according to the following:

ABBREVIATIONS

ASCII American standard code for information interchange file format
CGM Computer graphics metafile
ODS Output Delivery System
RTF Rich text file format

INTRODUCTION

This document applies to standards used for outputting tables, listings and figures. It is intended to provide specifications to guide the statistician or statistical programmer in setting up specifications for programming tables, listings and figures. These standards should be used in the absence of customer specific standards.

OUTPUT FILE NAMING CONVENTIONS

File names should only consist of uppercase letters, lowercase letters, digits (0 to 9) and underscores. A period should only be used to indicate a separator between the file name and the extension. No spaces, other special characters or punctuation marks are permitted.

As far as possible, output files should be in RTF format, although .DOC files are also permitted.

The program, program log and output file name should reflect the type and number of the statistical output. If this is not possible, then the output name should be at least as descriptive as possible. A prefix can be used to distinguish between a Table, Listing and Figure document ('T' for table, 'L' for listing and 'F' for figure). If there is only 1 digit in the number of the table, listing or figure in the place

Document: \\weedc-vnasc01\BIOSdata\F2G\F901318 
Author:  Version Number: 3.0
Version Date: 06Apr2023
Template No.: CS_TP_BS016 Revision 6 Reference: CS_WI_BS005
Effective Date: 02Dec2019

where 2 digits are possible, a leading zero should be added in the file name to make sorting consistent with the sequence (eg T14_3_01_1.rtf)

PAPER SIZE, ORIENTATION AND MARGINS

The size of paper will be Letter for the United States, otherwise A4.

The page orientation should preferably be landscape, but portrait is also permitted.

Margins should provide at least 1 inch (2.54 centimeters) of white space all around the page, regardless of the paper size.

The number of columns per page (linesize) should be 145 for A4 and 134 for Letter.

The number of rows per page (pagesize) should be 49 for A4 and 51 for Letter.

FONTS

The font type 'Courier New' should be used as a default for tables and listings, with a font size of 8.

The font color should be black. No **bolding**, underlining or *italics* should be permitted. Single spacing should be used for all text.

Figures should have a default font of "Times Roman", "Helvetica", or "Courier New".

This can be achieved by using the following options in SAS:

```
goptions  
gunit = pct  
cback = white  
colors = (black)  
hby = 2.4  
ftext = "TimesRoman"  
htext = 2.5  
device = cgmof971  
gaccess = gsasfile;  
filename gsasfile "...cgm";
```

HEADER INFORMATION

Headers should be defined as follows:

- The header should be placed at the top of the page (same place on each page) regardless of the size or orientation of the table or listing
- The customer name and protocol number should appear in row 1, left-aligned

Document:	\\weedc-vnasc01\BIOSdata\F2G\F901318\		
Author:		Version Number:	3.0
		Version Date:	06Apr2023
Template No.:	CS_TP_BS016 Revision 6	Reference:	CS_WI_BS005
Effective Date:	02Dec2019		

- The output identification number should appear in row 2, centered
- The output title should start in row 3, centered
- The output population should appear in row 4, centered. The population should be spelled out in full, e.g. Intention-to-Treat in preference to ITT.
- Row 5 should be a continuous row of underscores ('_') (the number of underscores should equal the linesize)
- Row 6 should be a blank line
- Mixed case should be used for titles
- The output titles should be designed so that they are arranged consistently through all outputs. For example, content (eg Vital Signs) followed by metric (eg Change from Baseline) e.g. Vital Signs – Change from Baseline.
- Titles should not contain quotation marks or footnote references
- The column headings should be underlined with a row of underscores ('_')
- Column headings spanning more than one column should be underlined and have underscores on either side of the title and should be centered
- Column headings containing numbers should be centered
- Column headings should be in sentence case
- In general, the population count should appear in the column header in the form "(N=XXX)"
- "Statistic" should be the column header over n, Mean, SE, n (%) etc.
- As a rule, all columns should have column headings.

TABLE AND LISTING OUTPUT CONVENTIONS

General:

- The first row in the body of the table or listing should be blank
- The left hand column should start in column 1. No indenting or centering of the output should occur.
- Rounding should be done with the SAS function ROUND.
- Numbers in tables should be rounded, not truncated.
- Alphanumeric output should be left aligned.
- Numbers should be decimal point aligned.
- Whole numbers should be right aligned.

Document: \\eedc-vnasc01\BIOSdata\F2G\F901318\ [Redacted]
Author: [Redacted] Version Number: 3.0
Version Date: 06Apr2023
Template No.: CS_TP_BS016 Revision 6 Reference: CS_WI_BS005
Effective Date: 02Dec2019

- Text values should be left aligned.
- The first letter of a text entry should be capitalized
- Listings of adverse events, concomitant medications, medical histories etc. should be sorted in chronological order, with earliest adverse event, medication or history coming first.
- The study drug should appear first in tables with treatments as columns
- In general, only present totals (across treatment groups) at baseline/randomization, and do not present them post randomization, unless the customer specifically requests it.
- If possible, include 100% frequencies in the table shell, so that it is clear what the denominator is for percentage calculations.
- The width of the entire output should match the linesize

Univariate Statistics:

- Statistics should be presented in the same order across tables (i.e., n, Mean, SD, Median, Minimum, Maximum)
- Table statistics should line up under the N part of the (N=XXX) in the table header. All decimal points should line up. If the minimum and maximum are output on one line as Minimum, Maximum then the comma should line up with the decimal point.
- If the original data has N decimal places, then the summary statistics should have the following decimal places:
Minimum and maximum: N
Mean, median and CV%: N + 1
SD: N + 2

Frequencies and percentages (n and %):

- Percent values should be reported inside parentheses, with one space between the count and the left parenthesis of the percentage. Parentheses should be justified to accept a maximum of 100.0 as a value and padded with blank space if the percent is less than 100.0. An example is given below:
77 (100.0%)
50 (64.9%)
0 (0.0%)
- Percentages will be reported to one decimal place, except percents <100.0% but >99.9% will be presented as '>99.9%' (e.g., 99.99% is presented as >99.9%); and percents < 0.1% will be

Document: \\weedc-vnasc01\BIOSdata\F2G\F901318\ [Redacted]
Author: [Redacted] Version Number: 3.0
Version Date: 06Apr2023
Template No.: CS_TP_BS016 Revision 6 Reference: CS_WI_BS005
Effective Date: 02Dec2019

presented as '<0.1%' (e.g., 0.08% is presented as <0.1%). Rounding will be applied after the <0.1% and >99.9% rule.

Eg (<0.1%)
(6.8%)
(>99.9%)

Percentages may be reported to 0 decimal places as appropriate (for example, where the denominator is relatively small).

- Where counts are zero, percentages of 0.0% should appear in the output.

Confidence Intervals:

- As a rule confidence intervals are output to one place more than the raw data, and standard deviations and standard errors to two places more than the raw data
- Confidence intervals should be justified so that parentheses displayed on consecutive lines of a table "line up".
- Boundary values of confidence intervals should be separated by a comma.
- Boundary values should be padded as necessary to accept negative values and to allow alignment of the decimal place.
- An example is given below:
(-0.12, -0.10)
(9.54, 12.91)

P-values:

- P-values should be reported to three decimal places, except values <1.000 but >0.999 will be presented as '>0.999' (e.g., 0.9998 is presented as >0.999); and values <0.001 will be presented as '<0.001' (e.g., 0.0009 is presented as <0.001). Rounding will be applied after the <0.001 and >0.999 rule

Ratios:

- Ratios should be reported to one more decimal place than the original data.

Spacing:

- There must be a minimum of 1 blank space between columns (preferably 2)

Denominators:

Document: \\weedc-vnasc01\BIOSdata\F2G\F901318\ [Redacted]
Author: [Redacted] Version Number: 3.0
Version Date: 06Apr2023
Template No.: CS_TP_BS016 Revision 6 Reference: CS_WI_BS005
Effective Date: 02Dec2019

- If a different count other than the population count is used for a denominator (within the table) to calculate percentages, there should be a row in the table that identifies that number “n”.
- Alternatively, a footnote should be included in each table with percentages to indicate the denominator for percentages.

Missing values

- A “0” should be used to indicate a zero frequency.
- A blank will be used to indicate missing data in an end-of-text table or subject listing.

FIGURE OUTPUT CONVENTIONS

- Figures should be provided in RTF files.
- The image should be clear and of high quality when viewed in the Word document, and when printed.
- In general, boxes around the figures should be used.

FOOTNOTE INFORMATION

Footers should be defined as follows:

- A continuous line of underscores (‘_’) will follow the body of the table or listing prior to any footnotes at the bottom of the page
- Table footnotes should appear directly after the body of the table
- The program path and name and version number (if applicable) should appear as footnote 1 at the bottom of the page
- The date/time stamp should appear as footnote 2 at the bottom of the page
- Footnotes should be left-aligned.
- Footnotes should be in sentence case.
- Only “typewriter” symbols are permitted – eg “*”, “\$”, “#”, “@”, “&” and “+”.
- The choice of footnote symbols should be consistent. E.g. if you have the footnote “# indicates last observation carried forward” for one table, the same symbol and footnote should indicate LOCF for all tables.

Document: \\eedc-vnasc01\BIOSdata\F2G\F901318\ [Redacted]
Author: [Redacted] Version Number: 3.0
Version Date: 06Apr2023
Template No.: CS_TP_BS016 Revision 6 Reference: CS_WI_BS005
Effective Date: 02Dec2019

- If text wraps across more than one line (for a note), the first letter for all lines of text after the first one will be indented to align beneath the first letter of the text in the first line.
- The page identification in the format Page X of Y (where Y is the total number of pages for the output) should appear in the first footnote, right aligned

Ordering of footnotes should be as follows:

- 1.) Source data listing reference, if necessary
- 2.) Abbreviations and definitions
- 3.) Formulae
- 4.) P-value significance footnote
- 5.) Symbols
- 6.) Specific notes

- Common notes from table to table should appear in the same order.
- The symbols should appear in the same order as what they are defined in the table or listing, from left to right.

PROGRAMMING INSTRUCTIONS

Programming instructions must appear at the end of each table or listing shell. Programming instructions, where necessary, should begin with the words "Programming Note" followed by a colon. These include notes on the output, reminders of how to handle missing values, repeat shells for similar tables etc.

Document: \\eedc-vnasc01\BIOSdata\F2G\F901318 [REDACTED]
Author: [REDACTED] Version Number: 3.0
Version Date: 06Apr2023
Template No.: CS_TP_BS016 Revision 6 Reference: CS_WI_BS005
Effective Date: 02Dec2019

F2G Ltd.
PROTOCOL F901318/0032

EXAMPLE

Customer Name - Protocol Number: _____

Table 14.1.1.1
Subject Disposition

Disposition	Number (%) of Subjects		
	Treatment		Total (N=XX)
	A (N=XX)	B (N=XX)	
Randomized	XX	XX	XX
Completed	XX (XX.X%)	XX (XX.X%)	XX (XX.X%)
Discontinued	XX (XX.X%)	XX (XX.X%)	XX (XX.X%)
Reasons for Discontinuation: XXXXXXXXXXXXX XXXXXXXXXXXXX	XX (XX.X%) XX (XX.X%)	XX (XX.X%) XX (XX.X%)	XX (XX.X%) XX (XX.X%)

SOURCE: Listing 16.2.1.1
Abbreviations / definitions
Formulae
F-values...
Symbols...
NOTE 1: Treatment A=XXXXXXXXXXXXXXXXXXXXX.
 B=XXXXXXXXXXXXXXXXXXXXX.
NOTE 2: ...

Page 1 of 1

- X:\CUSTOMER\COMPOUND\STUDY\BIOSTATISTICS\PRODUCTION\TABLES\T14_1_1_1_SAS.DDMMYYYY HH:MM

DATES & TIMES

Depending on data available, dates and times will take the form DDMMYYYY:hh:mm.

SPELLING FORMAT

English UK.

PRESENTATION OF VISITS

For outputs, visits will be represented as follows and in that order:

Long Name (default)	Short Name
Screening (Visit 1)	Screening
Baseline ^a	Baseline
Day 1 (Visit 2)	Day 1

Document: \\weedc-vnasc01\BIOSdata\F2G\F901318_____

Author: _____ Version Number: 3.0

Version Date: 06Apr2023

Template No.: CS_TP_BS016 Revision 6 Reference: CS_WI_BS005

Effective Date: 02Dec2019

F2G Ltd.
PROTOCOL F901318/0032

Long Name (default)	Short Name
Day 2 (Visit 3)	Day 2
Day 3 (Visit 4) * Day 3-5 will be presented under Day 3 (Visit 4)	Day 3
Day 5 (Visit 5)	Day 5
Day 7 (Visit 6) * Day 6-8 will be presented under Day 7 (Visit 6)	Day 7
Day 10 (Visit 7) * Day 9-11 will be presented under Day 10	Day 10
Day 14 (Visit 8)	Day 14
Day 17-18 (Visit 9)	Day 17-18
Day 21 (Visit 10)	Day 21
Day 24-25 (Visit 11)	Day 24-25
Day 28 (Visit 12)	Day 28
Day 35 (Visit 12a)	Day 35
Day 42 (Visit 13)	Day 42
Day 49 (Visit 13a)	Day 49
Day 56 (Visit 14)	Day 56
Day 70 (Visit 15)	Day 70
Day 84 (Visit 16)	Day 84
CRF End of Treatment (Visit 17)	CRF EOT

Document: \\ieedc-vnasc01\BIOSdata\F2G\F901318\ [Redacted]
 Author: [Redacted] Version Number: 3.0
 Version Date: 06Apr2023
 Template No.: CS_TP_BS016 Revision 6 Reference: CS_WI_BS005
 Effective Date: 02Dec2019

F2G Ltd.
PROTOCOL F901318/0032

Long Name (default)	Short Name
Derived End of Treatment ^b	DER EOT
Follow-up 4 Weeks after End of Treatment (Visit 18)	FU 4 WKS EOT
Unscheduled Visit XX.XX ^c	UNSCH XX.XX
Start of Extended Treatment ^d	ST EXT TRT
Extended Treatment Visit XX ^d	EXT TRT VXX
End of Extended Treatment ^d	END EXT TRT
Follow-up 4 Weeks after End of Extended Treatment ^d	FU 4WKS END EXT TRT
^a A Baseline visit will be programmatically added to outputs (where applicable) based on the derived baseline flag. ^b Derived End of Treatment visits will be programmatically added to outputs where applicable. ^c In chronological order in between scheduled visits, as applicable. ^d Extended Treatment visit will not be included in outputs but will form part of ADaM datasets.	

LISTINGS

All listings will be ordered by the following (unless otherwise indicated in the template):

- Baseline DRC-adjudicated disease category,
- Patient number,
- Date (where applicable).
- Prior Antifungal Therapyat Time of Enrollment to Olorofim

“Nature of response to prior antifungal therapy at time of enrollment to olorofim trial” in eCRF page “Pre-Study Course for Fungal Infection Under Study”.

CRF Page: Nature of response to prior antifungal therapy at time of enrollment to Olorofim trial?	(To be presented as) Subgroup “ Prior antifungal therapy response ”, categories:
---	---

Document: \\weedc-vnasc01\BIOSdata\F2G\F901318\ [Redacted]
 Author: [Redacted] Version Number: 3.0
 Version Date: 06Apr2023
 Template No.: CS_TP_BS016 Revision 6 Reference: CS_WI_BS005
 Effective Date: 02Dec2019

F2G Ltd.
 PROTOCOL F901318/0032

Refractory / Failing	→	“Active (Uncontrolled)”
Stable / Persistent	→	“Active (Stable)”
Patients with no response entered (missing) or where response is “Unable to judge” (since detail of unable to judge showed all patients had no therapy or too brief)	→	“No therapy/too brief”
Partial	→	“Improved”
Complete	→	“Improved”
Multiple	→	“Multiple”
Note: If we expect multiple responses per patient, use the worst outcome (i.e. worst=refractory/failing, then stable/persistent, unable to judge, partial, complete)		

- Immuno suppression status
- Programming note; summary of primary disease type shown below. Medical review and final subgroup categories confirmed in spreadsheet
 “Immunosuppression_F2G_ [redacted] [redacted]”

UDPTCoded	Coded
AIDS	ModIS
CF	ModIS
CGD	ModIS
GenMedical	LowIS
HemeMalig	HighIS
HSCT	HighIS
ImmuneDefect	ModIS
LungTx	ModIS
None	LowIS
NonHemeMalig	ModIS
OtherSOT	ModIS

Document: \\weedc-vnasc01\BIOSdata\F2G\F901318 [redacted]
 Author: [redacted] Version Number: 3.0
 Version Date: 06Apr2023
 Template No.: CS_TP_BS016 Revision 6 Reference: CS_WI_BS005
 Effective Date: 02Dec2019

F2G Ltd.
 PROTOCOL F901318/0032

